3.2.3 Exploratory Outcome Measures

- 1. Mean time from scheduled pick-up at subject residence (DBS tests) or blood draw facility (plasma sample) to arrival at the laboratory (hours) at all applicable test points throughout the study period
- 2. Number of mobile technology failures, sample collection failures, sample delivery failures, and sample viability failures.
- 3. Sensitivity, specificity and predictive values of CMV detection in DBS versus plasma testing
- 4. Number and type of key transplant characteristics in randomized subjects and observational subjects (Section 5.1)
- 5. Describe the baseline patient demographics of randomized cohort and observational cohort.
- 6. Number of participants with end-organ CMV disease (possible and proven/possible) at 1 year after HCT in randomized subjects and observational subjects
- 7. Describe local provider CMV treatment viral load treatment thresholds
- 8. Describe local provider CMV monitoring interval recommendations
- 9. Report composite scores of different variables of subject and provider satisfactions according to the 5-point Likert scale questionnaires.

4 STUDY DESIGN

[figure not shown]
This is a randomized clinical trial to assess whether self-collection of samples (DBS) that are mailed for testing to a central laboratory will improve the compliance with the clinical recommendation of weekly CMV testing of HCT recipients. 150 allogeneic HCT recipients \geq 15 years of age, who are considered by their transplant teams to be at risk for late CMV disease and who are clinically recommended to continue CMV monitoring after day 100 post-transplant, will be randomized (2:1) to subject self-collected DBS CMV monitoring with mobile technology support or standard of care with office-based testing. Randomization will occur when discharge from the transplant service is imminent, generally near day 100 post-transplant (enrollment window day 60-180 post-transplant). DBS self-collections will start the week after discharge. More than 85% of late CMV disease occurs within the first year after HCT ³⁷. While most patients are discharged to long-term primary care providers approximately 100 days after HCT, some may be discharged earlier, and some may stay longer with the transplant team due to complications. These latter patients are often at particularly high risk for late CMV complications and thus are important candidates for participation in this trial. For this reason, study entry is allowed up to 180 days (~6 months) after HCT and the duration of study participation is anticipated to be within a range of 26 weeks to 43 weeks.

The transplant centers participating in this study have either a standard process where transplant recipients are offered to sign a consent to allow data from their charts to be accessed for retrospective trials or a waiver of additional consents for accessing charts for retrospective trials. This offers an opportunity to assess whether the study sample is representative of HCT population as a whole and to obtain a population-based estimate of later CMV disease. Therefore, clinical charts from an additional 450 HCT recipients (Observational Cohort) who meet eligibility criteria and have already consented for retrospective studies at the enrolling sites but are not participating in the DBS testing for CMV will be reviewed for the incidence and timing of CMV disease, morphologic relapse of the underlying disease, and death. Data from these subjects will be used to assess whether the randomized study sample is representative of the DBS study population and to obtain a population-based estimate of late CMV disease.

OBSERVATIONAL COHORT, n=450

¹Quarterly contacts will be scheduled from the date of transplant, not based on the date of enrollment.

X

4.1 Randomized Cohort

Following consent, subjects in the DBS arm of the study will be asked to perform weekly DBS collection starting the week after discharge, once appropriate training has been provided (collection can be performed by a caregiver as long as appropriate training has been completed). Weekly reminders will be sent either as email or text messages. DBS samples will be mailed directly to the central lab (University of Washington) via pre-paid overnight mail (pick-up can be scheduled via the website or by phone through website) by the subjects. Results will be transmitted via a secure server to participating site staffs. The research staff will then contact the subjects' treating physicians via phone/fax notifying of positive results. The subjects will receive a notification via the study web portal when their positive CMV test results are available with a link to the secure website that can be used to access them. Text message reminders have been effective in randomized trials of medication adherence ^{5,38,39}, but too frequent reminders may be counterproductive. The web/mobile technology employed in this trial allows subjects to select method of electronic reminders (email and/or text message) and day and time of weekly electronic reminders. At minimum, one reminder will be sent before the recommended test.

In addition to the DBS Self-Collection Kits, subjects will be provided with Confirmatory Whole Blood Collection Kits for a plasma CMV PCR test (one 6 ml EDTA tube and a DBS self-collection kit with shipping material). When subjects are notified of a positive DBS result (a reminder will be provided with the notification of positive test results) they will take the Confirmatory Whole Blood Collection kit to their clinical blood draw facility and get their samples collected as soon as possible. The clinical laboratory staff will draw the additional blood and use the pre-paid FedEx shipping kit to send the sample to the University of Washington Molecular Virology Laboratory for testing. Decisions whether to administer preemptive treatment based on plasma viral load results will be made by the primary care provider of the subject. At the time of office-based blood draw for research confirmatory plasma CMV PCR, the subject will perform an additional DBS test, which will be sent together with the plasma sample to the central lab. These samples will provide additional virologic data to assess performance of the DBS assay. This method has been used successfully in a recently completed phase III trial ²².

Training of participants on the DBS self-collection procedures will include three training sessions with a study coordinator. The first session will describe, observe, and provide guidance on DBS self-collection procedures and web/mobile technology. The second session will be a supervised session with the subject to observe and answer questions. It is preferable that supervised DBS trainings with a study coordinator are done in-person; however, if this is

not possible these supervised trainings may be completed remotely via video conferencing as an option (See MOP for details and instructions). The third session will be unsupervised with the subject performing the testing in their home or temporary residence nearby the transplant center This training session will be followed up with a phone call or in-person check-in and a questionnaire to assess understanding. At each session, the subject will have written instructions on performing the DBS testing and utilizing the web/mobile technology available for their reference. Each DBS training session requires the completion of a DBS collection. The study coordinator will be available to provide additional training session as needed. In addition, DBS collection instructional video is available on the study website. Prior to discharge from the transplant care team, study personnel must confirm that the subject demonstrates proficiency in DBS sample collection and use of the study website.

The mobile technology will consist of a notification system that sends weekly reminders by email and/or text message determined by the subject's preference to the subject to complete DBS self-collection procedures. The notifications are sent from a web-based, 21 CFR 11-compliant electronic data capture system created and maintained by The Emmes Company. The subject will log into the system on a computer or mobile device with internet access to set up study reminders and record sample collection and shipment information. The system will also house IRB-approved training materials and the web address of the United States Postal Services (USPS) so that shipments may be scheduled.

Subjects who are enrolled in the control arm of the randomized study will continue to receive their office-based CMV plasma testing as recommended by standard of care.

Quarterly follow-up contacts will be made with the primary care physicians of all randomized subjects enrolled in the study to obtain each subject's medical record. Data from each subject's medical record on immunosuppression, CMV disease status, any interim use of antiviral therapy for CMV disease or plasma reactivation, clinically recommended CMV test interval, any hospitalization record, relapse, and survival status will be collected.

4.2 Observational Cohort

A parallel observational contemporary cohort will be established of up to 450 transplant recipients who are eligible for enrollment but declined participation as part of the randomized cohort and/or have consented at their site to have data from their charts abstracted for retrospective studies and meet entry criteria for the randomized trial. Selection of eligible subject charts will be based on similar criteria to the randomized study and will include subjects who qualified for the study but did not provide consent. Eligible participants meeting those criteria will be included in an observational study.

To allow data extraction for this observational cohort, each participating site must have on record with their IRBs either:

• A general consent for the review of medical records for retrospective studies that can be utilized for this activity, or

A waiver of additional consent for the review of medical records for retrospective studies linked to this protocol. Data from each subject's medical record on immunosuppression, steroid use, CMV disease status, any interim use of antiviral therapy for CMV disease or plasma reactivation, clinically recommended CMV test interval at time of discharge, morphological relapse, and survival status will be collected at approximately one year post transplant date. Data to be abstracted from the charts will cover an equivalent length of time as those subjects enrolled in the randomized study (i.e. until 1 year after HCT).

5 STUDY ENROLLMENT AND WITHDRAWAL

Approximately, 150 allogeneic HCT recipients \geq 15 years of age, who are considered by their transplant team to be at risk for late CMV disease as defined in the entry inclusion criteria and recommended to continue CMV monitoring after 100 days post-transplant, will be enrolled in the study. These individuals will be randomized (2:1) to subject collected DBS CMV monitoring with mobile technology support or standard care with office-based testing.

Recruitment of subjects will follow local recruitment and enrollment policies and procedures. The study sites will request a waiver of informed consent and a waiver of HIPAA Authorization for pre-screening purposes (to determine CMV sero- and reactivation status) from their local Institutional Review Board (IRB). Upon approval of both waivers, research staff will review the electronic medical records to pre-screen subjects who will undergo or have undergone an allogeneic hematopoietic cell transplant (HCT). Pre-screening will be done by trained and experienced research staff who will review the electronic charts using a standardized screening tool. In addition, potential subjects may be identified by the attending physician (or team) based on the eligibility criteria approximately one month prior to anticipated discharge from the primary transplant team. If a subject is identified as meeting the inclusion/exclusion criteria, the PI or designee will explain the study and will seek informed consent to study participation.

Retention efforts will focus on the interval between enrollment/randomization and discharge from the transplant team and start of diagnostic monitoring. Since adherence is a key study endpoint, direct contact between site personnel and study subjects will be kept as equal as possible between the two arms to avoid biasing the comparison of CMV monitoring adherence.

5.1 Subject Inclusion Criteria

5.1.1 Randomized Cohort

- Must be ≥ 15 years of age at the time of enrollment
- Must be able to provide written consent and complete the informed consent
- Must have received allogeneic hematopoietic cell transplantation within 60-180 days prior to randomization
- CMV seropositive or had a donor who was CMV positive

DMID/NIAID/NIH CONFIDENTIAL

- One or both of the following:
 - CMV event¹ within the first 100 days post-transplant requiring anti-viral treatment
 - Receipt of CMV prophylaxis² (for at least 30 days) prior to randomization. Continuation of letermovir or acyclovir/valacyclovir (high and low dose) prophylaxis after day 100 per institutional standard of care is permitted.

¹ CMV event defined as DNA detection or disease

²*Anti-viral treatment or prophylaxis includes ganciclovir, valganciclovir, foscarnet, letermovir, maribavir or acyclovir/valacyclovir (high and low dose)*

- Direct availability to the internet either by a computer in the residence or a smart phone
- Had at least one or more of these conditions:
 - HLA mismatch³
 - Umbilical cord blood source⁴
 - \circ GVHD⁵
 - T-cell depletion⁶

³Human leukocyte antigen (HLA)-related(sibling) donor with at least one mismatch at one of the following three HLA-gene loci: HLA-A, -B or -DR, Haploidentical donor, Unrelated donor with at least one mismatch at one of the following four HLA-gene loci: HLA-A, -B, -C and -DRB1

⁴Use of umbilical cord blood as stem cell source

⁵Acute or chronic GVHD requiring topical steroid for GI GVHD and/or systemic steroid treatment (≥ 1 mg/kg/day of prednisone or equivalent dose of another corticosteroid) within 6 weeks prior to enrollment

⁶Subjects who have received partial or full T-cell depletion (with or without GVHD). T-cell depletion can be given as either ex-vivo or in-vivo for GVHD prophylaxis. T-cell depleting agents include, but are not limited to, anti-thymocyte globulin (ATG) and alemtuzumab.

5.1.2 Observational Cohort

- Must be ≥ 15 years of age at the time of enrollment
- Must have one of the following:
 - Consented for retrospective studies at their transplant center, or
 - Be included under the auspices of the site's IRB approved waiver of additional consent for retrospective studies
- Must have received allogeneic hematopoietic cell transplantation during or within 1 year prior to the conduct of the randomized trial (defined as time during which randomization is done).
- CMV seropositive or had a donor who was CMV positive
- One or both of the following:
 - CMV event¹ within the first 100 days post-transplant requiring anti-viral treatment.
 - Receipt of CMV prophylaxis² (for at least 30 days) prior to registration. Continuation of letermovir prophylaxis or acyclovir/valacyclovir (high and low dose) after day 100 per institutional standard of care is permitted.

¹ CMV event defined as DNA detection or disease

²*Anti-viral treatment or prophylaxis includes ganciclovir, valganciclovir, foscarnet, letermovir, maribavir or acyclovir/valacyclovir (high and low dose)*

- Meet one or more criteria of the following:
 - o HLA mismatch³
 - Umbilical cord blood source⁴
 - \circ GVHD⁵

DMID/NIAID/NIH CONFIDENTIAL

\circ T-cell depletion⁶

³Human leukocyte antigen (HLA)-related(sibling) donor with at least one mismatch at one of the following three HLA-gene loci: HLA-A, -B or -DR, Haploidentical donor, Unrelated donor with at least one mismatch at one of the following four HLA-gene loci: HLA-A, -B, -C and -DRB1

⁴Use of umbilical cord blood as stem cell source

⁵ Acute or chronic GVHD requiring topical steroid for GI GVHD and/or systemic steroid treatment (≥ 1 mg/kg/day of prednisone or equivalent dose of another corticosteroid) within 6 weeks prior to enrollment

⁶ Subjects who have received partial or full T-cell depletion (with or without GVHD). T-cell depletion can be given as either ex-vivo or in-vivo for GVHD prophylaxis. T-cell depleting agents include, but are not limited to, anti-thymocyte globulin (ATG) and alemtuzumab.

5.2 Subject Exclusion Criteria

5.2.1 Randomized Study

- Inability to fully comprehend the study website and study procedures
- Any other condition, which in the opinion of the investigator would interfere with successful completion of this clinical trial
- Morphological relapse (bone marrow or peripheral blood blast) prior to registration.

5.2.2 Observational Cohort

- Did not meet all inclusion criteria
- Morphological relapse (bone marrow or peripheral blood blast) prior to registration.

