5.3 Treatment Assignment Procedures

5.3.1 Randomization Procedures

Subjects will be randomized in a 2:1 ratio to subject-collected DBS CMV monitoring with mobile technology support (n=100) or standard care with office-based testing (n=50). Additional subjects will be enrolled as retrospective observational controls and will not be randomized (n=450). The list of randomized treatment assignments will be prepared by statisticians at The Emmes Corporation (Emmes) and included in the enrollment module of Emmes' Internet Data Entry System (IDES). IDES will assign each subject a study arm from the list after demographic (date of birth, race/ethnicity, and sex) and eligibility data have been entered into the system. Randomization will be stratified by transplant site and subject's perceived ease of access to blood draw facility. Observational cohort will be enrolled in IDES after the required demographic and eligibility information are entered. Instructions for use of the enrollment module are included in the IDES User's Guide. Manual back-up randomization procedures are provided in the MOP for use in the event that the site temporarily loses access to the Internet or the online enrollment system is unavailable.

Subject IDs will be assigned to potential subjects, who have documented informed consent by signing an Informed Consent form, as they are screened. The subject ID will be used for all communications with outside institutions to ensure confidentiality.

Subjects who are randomized and drop out of the study prior to beginning follow-up (first scheduled test both arms) will be replaced. Over-enrollment is allowed to accommodate competitive enrollment and accommodate replacement subjects.

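### For observational charts registered after day 180, relapse, GVHD and prophylaxis criteria dated from registration or enrolment select on follow-up events and conflict with the day 60-180 window stated elsewhere

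*Protocol*

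**What the plan says.** **Randomised cohort (Protocol 5.1.1, 5.2.1).** Eligibility is fixed in post-transplant time: "Must have received allogeneic hematopoietic cell transplantation within 60-180 days prior to randomization". Relapse before registration excludes, and registration precedes the start of surveillance.

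**Observational cohort (Protocol 5.1.2, 5.2.2; repeated in SAP 4.3.1.2 and 4.3.2.2).** The transplant condition is "Must have received allogeneic hematopoietic cell transplantation during or within 1 year prior to the conduct of the randomized trial", with no day 60-180 limit. Three criteria look back from study entry:
- relapse: "Morphological relapse (bone marrow or peripheral blood blast) prior to registration";
- prophylaxis, also dated from registration;
- steroid-requiring GVHD: "within 6 weeks prior to enrollment".

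One criterion is tied to the transplant itself: "CMV event¹ within the first 100 days post-transplant requiring anti-viral treatment".

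**Nature of the cohort.** Protocol 5.3.1 states: "Additional subjects will be enrolled as retrospective observational controls". Section 4.2 collects their data at about one year after transplant. Section 4 says that the charts "will be reviewed for the incidence and timing of CMV disease, morphologic relapse of the underlying disease, and death", so relapse is also something to be observed.

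**Text pointing the other way.** Protocol 7.2 gives an enrolment window of day 60-180 and applies its enrolment procedures to the observational cohort too. Appendix C and SAP Table 1 mark observational eligibility in the screening column for day 60-180. SAP 4.5.3 records prophylaxis from transplant to day 100.

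**Use of the cohort.** It serves exploratory objectives 4 and 5, the comparison with non-participants in Protocol 11.1.2, and Gray's test at 5% of All Randomized against Observational in SAP 9.3. SAP Table 22 counts CMV disease from discharge and has an Observational column.

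**The concern.** For a randomised subject, registration comes before follow-up, so a criterion dated from registration is a baseline criterion. For a chart registered later, the same wording reaches into follow-up. A patient who relapses on day 250 and is registered on day 365 is excluded. A randomised subject who relapses on day 250 stays in, with the relapse recorded under Protocol 7.5 and 7.6. The GVHD look-back then falls at a different post-transplant time from that of the randomised cohort, and prophylaxis first given late could qualify a chart.

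At stake is whether the observational cohort describes the population from which the randomised sample came. Among late-registered charts, relapse between discharge and registration is zero by construction. Deaths after such relapses go with it, and death is the competing event in SAP 9.3. A common time origin in the analysis does not repair this, because the excluded charts are not in the data.

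**Working it through.** **1. Time anchor of each observational criterion**

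| Criterion | Anchor | Affected by late registration? |
|---|---|---|
| Relapse (exclusion) | registration | yes; it excludes on its own |
| GVHD with steroids | 6 weeks before enrolment | partly; one of four alternatives |
| Prophylaxis, at least 30 days | registration | partly; one of two alternatives |
| CMV event | day 0-100 after HCT | no |
| HLA mismatch, cord blood | transplant | no |
| T-cell depletion | no registration-based window | no |

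**2. Is late registration possible?** Assume that charts are not registered before randomisation opens. A patient transplanted *d* days before opening is then at day *d* or later when first registrable. Section 5.1.2 admits *d* up to 365. For *d* = 181 to 365 the earliest possible registration is day 181 to 365, outside the day 60-180 window. For these patients 5.1.2 and 7.2 cannot both be met. For later transplants, late registration is possible but not required.

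**3. Length of the extra exclusion period.** With registration at day 365, relapse excludes for an additional 365 - 180 = 185 days (landmark day 180) to 365 - 60 = 305 days (landmark day 60).

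**4. The plan's own figures.** The 450 has no derivation and the plan gives no relapse rate. The nearest stated figure is the 330 subjects in Protocol 11.1.2 for 8% against 2% (one-sided 0.05, 80% power). With mean proportion 0.05, n per arm = [1.645√(2 × 0.05 × 0.95) + 0.842√(0.08 × 0.92 + 0.02 × 0.98)]² / 0.06², which rounds up to 163. The total is 326, within 3% of 330. It has no bearing on this point except to show that 8% is the plan's working rate.

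**5. Illustrative bias.** Let *f* be the fraction of otherwise eligible patients excluded for relapse after the landmark, and RR the CMV disease risk in relapsers relative to non-relapsers. Both are assumptions. If the whole population has an 8% rate and non-relapsers have rate *q*, then (1 - *f*)*q* + *f* × RR × *q* = 0.08. The observational estimate is *q* = 0.08 / (1 - *f* + *f* × RR).

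| *f* | RR 0.5 | RR 1 | RR 2 | RR 3 |
|---|---|---|---|---|
| 5% | 8.2% | 8.0% | 7.6% | 7.3% |
| 10% | 8.4% | 8.0% | 7.3% | 6.7% |
| 20% | 8.9% | 8.0% | 6.7% | 5.7% |
| 30% | 9.4% | 8.0% | 6.2% | 5.0% |

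Example: 0.08 / (0.8 + 0.2 × 3) = 0.08 / 1.4 = 5.7%.

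The 95% half-width at 8% with 450 charts is 1.96√(0.08 × 0.92 / 450) = 2.5 points. The largest shift is 8.0 - 5.7 = 2.3 points for *f* up to 20%, and 8.0 - 5.0 = 3.0 points at *f* = 30% with RR 3.

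**6. Charts lost.** Reaching 450 while excluding a fraction *f* drops 450/(1 - *f*) - 450 patients: 50 at 10%, 113 at 20%. These counts also rest on the assumed *f*.

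**The case against.** The strongest reply is that abstracting a chart late is not the same as registering it late. Protocol 4.2 describes a contemporary cohort that includes patients who declined the trial. Such a patient can be registered at discharge and the chart read at one year. Section 7.2, Appendix C and SAP Table 1 all place observational enrolment or eligibility at day 60-180, and Protocol 11.3 makes the one-year look-back a contingency. This stands. A reader might infer from the word retrospective that every chart is registered at one year; the documents do not say so. It does not help transplants more than 180 days before opening, which 5.1.2 still admits.

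A reader might also infer that all the eligibility criteria fail. They do not. GVHD and prophylaxis are only alternative routes in, the remaining criteria are safe, and the day 0-100 prophylaxis record in SAP 4.5.3 weakens the prophylaxis example. It also shows that the criterion and the recorded variable use different windows.

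Nor is every relapsing randomised subject retained. Protocol 5.3.3 allows withdrawal for relapse before surveillance starts and on starting end-of-life care, and SAP 9.3 ends CMV follow-up at withdrawal. The asymmetry therefore concerns relapse after surveillance begins.

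Finally, the illustrated shift stays inside the 2.5-point half-width for exclusion up to 20%. That is correct, but a systematic shift does not shrink as charts are added.

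**Conclusion.** The concern holds for charts registered after the day 60-180 window. For these, the relapse exclusion, and to a lesser degree the GVHD and prophylaxis criteria, make eligibility depend on events during follow-up. The wording also conflicts with Protocol 7.2 and Appendix C. Late registration is unavoidable for transplants more than 180 days before opening, on the assumption that registration does not start before randomisation does.

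The effect is confined to exploratory objectives 4 and 5 and the randomised-versus-observational CMV comparison. Size and direction cannot be determined: the share of late charts, the relapse rate and the CMV risk after relapse are not in the documents. The 5.7-8.9% range is an illustration under assumed inputs, not an estimate.

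It would be tempting to call the cohort an invalid check on the randomised sample. The documents do not support that, since many charts may be registered in the window and the bias may be small. The primary randomised comparison is not affected.

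**What to change.** In Protocol 5.1.2 and 5.2.2 and SAP 4.3.1.2 and 4.3.2.2, define an index date for observational charts that matches the point at which randomised subjects are judged eligible: at or near discharge, within day 60-180 after HCT. Randomised eligibility is fixed at randomisation, shortly before discharge, so the definition should keep the two points close. Then:

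- judge relapse, GVHD and prophylaxis as of the index date;
- keep later relapse as an outcome and start CMV follow-up at the index date;
- reconcile the text with Protocol 7.2, Appendix C and SAP 4.5.3;
- apply the index-date criteria as an analysis restriction to charts already registered;
- report days from HCT to registration, which SAP Table 12 already plans for this cohort, to show how late registration was;
- where screening records allow, reconsider charts rejected only for relapse after the index date.

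The cost is wording changes, modest chart work and some reclassified charts. Protocol 4.2 lists the monitoring interval at discharge but not explicitly a discharge date, so that date may need abstraction. Nothing shows that records of rejected charts were kept, so the last step may be only partly possible.
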